## 9.3.2 Analysis of Key Secondary Variables

### 9.3.2.1 Definition of Variables

Pulmonary exacerbation (PEX): A PEX is defined as a new event or change in antibiotic therapy (IV, inhaled, or oral) for any 4 or more of the following signs/symptoms:

- Change in sputum
- New or increased hemoptysis
- Increased cough
- Increased dyspnea
- Malaise, fatigue, or lethargy
- Temperature above 38°C (equivalent to approximately 100.4°F)
- Anorexia or weight loss
- Sinus pain or tenderness
- Change in sinus discharge
- Change in physical examination (PE) of the chest
- Decrease in pulmonary function by 10%
- Radiographic changes indicative of pulmonary infection

The **PEX analysis period** will include the time from the first dose date of study drug until the last efficacy assessment, which may be collected up to the Week 24 Visit or the earlier of Day 169 and the end of study participation if subject does not have the Week 24 Visit.

The number of PEX through Week 24 is then defined as the total number of PEX for each treatment group during the PEX analysis period.

Sweat chloride (SwCl): the SwCl value for a given visit will be calculated as the mean of the non-missing sweat chloride measurements obtained on the left and right arms at that visit. If one of the two arm measurements at a time point is missing, the other will be used as the mean. A volume  $\geq 15$   $\mu\text{L}$  is required for an accurate determination of sweat chloride. Any results reported as having volume  $< 15$   $\mu\text{L}$  will be considered missing. Any sweat chloride values reported as  $< 10$  mmol/L or  $> 160$  mmol/L will be considered missing.

Cystic Fibrosis Questionnaire-Revised (CFQ-R): The CFQ-R is a validated CF-specific instrument that measures quality-of-life domains. This study utilizes three different versions of CFQ-R:

- CFQ-R for Children ages 12 and 13
- CFQ-R for Adolescents and Adults (subjects 14 years and older)
- CFQ-R for Parents/Caregivers (subjects 13 years and younger)

In all three versions, specific question belonging to a domain is scored 1, 2, 3, or 4. The CFQ-R domain score, e.g., physical domain score or respiratory domain score, is defined as a scaled score as follows:

Scaled score for a domain =  $100 \times (\text{mean (scores of all questions in the domain)} - 1)/3$ , where the score from a negatively phrased question is first reversed, i.e., reversed score =  $5 - \text{actual score}$ , so that 1 always represents the worst condition and 4 the best condition. The (scaled) domain score ranges from 0 (worst condition) to 100 (best condition). The scaled score for a specific domain will not be calculated if more than half of the questions in the domain have missing scores.

The (scaled) domain score from the CFQ-R for Children ages 12 and 13 and for Adolescent and Adults will be pooled for the analysis purpose.

Body mass index (BMI): the BMI at each visit is calculated using the weight and height at each visit as follows:

$$\text{BMI} = \frac{\text{Weight (kg)}}{\text{Height (m}^2\text{)}}$$

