**Table 3-2 Study VX17-659-102: Treatment Period and Safety Follow-up Visit**

Event/Assessment a	Day 1	Day 15 (± 3 Days)	Week 4 (± 5 Days)	Week 8 (± 5 Days)	Week 12 (± 5 Days)	Week 16 (± 5 Days)	Week 20 (± 5 Days)	Week 24 (± 5 Days)	ETT Visit b	Safety Follow-up Visit 28 (± 7) Days After the Last Dose of Study Drug (If Applicable) c
Clinic visit	X	X	X	X	X	X		X	X	X
Telephone contact							X d			
Inclusion and exclusion criteria confirmation	X									
CFQ-R e	X		X	X	X	X		X	X	X
Weight and height f	X	X	X	X	X	X		X	X	X
Ophthalmologic examination								X g	X g	X g

a All assessments will be performed before dosing unless noted otherwise.

b If the subject prematurely discontinues study treatment, an ETT Visit should be scheduled as soon as possible after the decision to discontinue treatment. Subjects who prematurely discontinue treatment will continue to complete all scheduled study visits for assessments following completion of the ETT Visit (Section 9.1.4).

c The Safety Follow-Up Visit is required for all subjects, unless the subject completes the Week 24 Visit and has enrolled in a separate open-label study within 28 days after the last dose of study drug (Section 9.1.3). If an ETT Visit occurs 3 weeks or later following the last dose of study drug, then the ETT Visit replaces the Safety Follow-up Visit (Section 9.1.4).

d Telephone contact will be made to assess the subject’s status, any AEs, concomitant medications, treatments, and procedures.

e The CFQ-R, [REDACTED] must be completed before any other assessments scheduled at relevant visits. Refer to Section 11.6.3 and [REDACTED]

f Weight and height will be measured with shoes off. Following screening, height will be collected only for subjects ≤21 years of age on the date of informed consent.

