#### 9.1.1.3 Extension of Screening Period Window

A subject may have the Screening Period window extended by 2 weeks for the following reasons:

- Repetition of the Screening Period assessments (Section 9.1.1.1)
- Unexpected operational or logistic delays, or to meet the eligibility criteria
- Scheduling of ophthalmologic examination (for subjects <18 years of age on the date of informed consent, [Section 11.7.6](#))
- 28-day washout period for subjects who have been on an investigational or commercially available *CFTR* modulator (e.g., TEZ/IVA, IVA [Kalydeco], LUM/IVA [Orkambi]; see [Table 9-2](#)).

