### 9.1 General Considerations

The Schedule of Assessments is provided in Section 3 of CSP. The precision standards for reporting safety and efficacy variables are provided in an internal Biometrics document that specifies the programming rules including the precision for derived variables.

**Continuous variables** will be summarized using the following descriptive summary statistics: the number of subjects (n), mean, SD, median, minimum value (min), and maximum value (max).

**Categorical variables** will be summarized using counts and percentages. Percentages will be presented to 1 decimal place.

**Baseline value**, unless otherwise specified, is defined as the most recent non-missing measurement (scheduled or unscheduled) collected before the first dose of study drug in the Treatment Period.

**Absolute change** from baseline will be calculated as post-baseline value - baseline value.

**Relative change** from baseline will be calculated as (post-baseline value - baseline value)/baseline value.

**Treatment-emergent (TE) period** will include the time from the first dose of study drug in the Treatment Period until 28 days after the last dose of study drug or to the completion of study participation, whichever occurs first.

Completion of study participation for each individual subject is defined as one of the following:

- For subjects who complete the Treatment Period and enter an open-label study within 28 days of the Week 24 Visit: the Week 24 Visit
- For subjects who complete the Treatment Period and do not enter an open-label study within 28 days of the Week 24 Visit: the Safety Follow-up Visit
- For subjects who prematurely discontinue study drug treatment but do not withdraw consent (and assent, as applicable): the latest of the Week 24 Visit, Early Termination of Treatment Visit, or Safety Follow-up Visit (if required)
- For subjects who withdraw consent or assent: date of withdrawal of consent or assent, whichever is earlier (CSP Section 9.9)

If subjects are lost to follow-up (CSP Section 9.1.5), the date of completion of study participation will be defined as the date of the last contact.

**Unscheduled visits:** Unscheduled visit measurements will be included in analysis as follows:

- 1) In scheduled visit windows per specified visit windowing rules
- 2) In the derivation of baseline and last on-treatment measurements

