- 3) In the derivation of maximum and minimum values during TE period, and maximum and minimum change from baseline values during TE period for safety analyses
- 4) In individual subject data listings as appropriate

**Visit windowing rules:** The analysis visit windows for protocol-defined visits are provided in [Appendix A](#).

**Incomplete/missing data** will not be imputed, unless otherwise specified.

**Outliers:** No formal statistical analyses will be performed to detect or remedy the presence of statistical outliers, unless otherwise specified.

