### **9.3 Efficacy Analysis**

All efficacy analyses described in this section will be based on the FAS, unless otherwise specified.

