### 9.3.3.2 Analysis Method

Time-to-first PEx through Week 24: Time-to-first PEx will be analyzed using the Cox regression model. The model will include a fixed effect for treatment, as well as continuous baseline ppFEV1, age at screening (<18 versus ≥18 years of age), and sex (male versus female) as covariates. Additionally, the Kaplan-Meier method will be used to produce a graphical presentation of the cumulative exacerbation-free rate for each treatment group and to estimate the cumulative exacerbation-free rate by treatment group.

[figure not shown]
Note: If the number of events is <5 in either treatment group, Cox regression will not be performed and the analysis of the time-to-first event will be restricted to the Kaplan-Meier method.

Absolute change in BMI z-score from baseline at Week 24 (for subjects ≤20 years of age at Baseline): Analysis of this variable will be based on an MMRM similar to the analysis of the primary efficacy variable, excluding the covariate of age at screening (<18 versus ≥18 years of age), for subjects ≤20 years of age at Baseline. Data obtained from Day 15, Week 4, Week 8, Week 12, Week 16, and Week 24 Visits will be included in the model.

Absolute change in body weight from baseline at Week 24: Analysis of this variable will be based on an MMRM similar to the analysis of the primary efficacy variable. Data obtained from Day 15, Week 4, Week 8, Week 12, Week 16, and Week 24 Visits will be included in the model.

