**Table 12-1 Analysis Visit Windows for Safety and Efficacy Assessments**

Assessment	Visit 	Target Study Day	Analysis Visit Window (in study days) 
Weight, Height and BMI (and the corresponding z-score)	Day 1 (Baseline)	1	≤1
	Day 15	15	(1, 22]
	Week 4	29	(22, 43]
	Week 8	57	(43, 71]
	Week 12	85	(71, 99]
	Week 16	113	(99, 141]
	Week 24	169	(141, 183]
	Safety Follow-up	Not applicable	>183

Notes:

 Visit name for analysis purpose is used to report data in tables and figures.

 The analysis visit windows will be applied using the following rules for both scheduled and unscheduled visits:

- If no numerical measurement is available within a visit window, the measurement will be considered missing for the visit.
- If there is more than 1 numerical measurement available within a visit window, use the following rules:
  - The measurement closest to the target day will be used; or
  - If there are multiple measurements with the same distance from the target day, the latest measurement will be used.

 For lab, ECG and vital sign measurement collected on the date of first dose of study drug, if it cannot be determined whether the measurement is before or after the first dose:

- Scheduled measurement will be treated as pre-dose observation.
- Unscheduled measurement will be treated as post-dose observation.

Derived Variables:

- Age (in years) at first dose date and nominal visit (for demographics, listing and the calculation of [percent] predicted spirometry variables):
 

Obtain the age at informed consent (in days) in “yy, mm” format (e.g., 24 years, 6 months) from the Vital Signs (VS) page at the Screening Visit, and add 0.5 month to convert to days.

Obtain the informed consent date.

Then age (in years) at first dose or nominal visit = [(first dose date or nominal visit date – informed consent date) in days + age at informed consent (in days)]/365.25.
- Age (in months) at nominal visit (for use in calculation of BMI and weight z-score):
 

Obtain the age at informed consent (in months) in “yy, mm” format (e.g., 24 years, 6 months) from Vital Signs (VS) page at the Screening Visit.

Obtain the informed consent date.

Then age (in months) at nominal visit = integer part of {(age at informed consent (in months) + 0.5 + diff(first dose date or post-baseline visit date, informed consent date) in months)} + 0.5.
- Missing first dose date or last dose date
 

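### Does deriving BMI from the height at each visit leave subjects over 21 without a post-baseline BMI?

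*SAP*

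**What the plan says.** SAP 9.3.2.1 defines the variable: "the BMI at each visit is calculated using the weight and height at each visit as follows". The formula carries no age condition. SAP 9.3.2.2 puts Day 15 and Weeks 4, 8, 12, 16 and 24 into the BMI model, and SAP 9.3 sets the population: "All efficacy analyses described in this section will be based on the FAS, unless otherwise specified".

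Footnote f of Protocol Table 3-2 limits one of the two inputs: "Following screening, height will be collected only for subjects ≤21 years of age on the date of informed consent". Protocol 11.6.2 repeats this. Weight is scheduled for everyone on Day 1 and at each of those six visits. Enrolment starts at 12 years with no upper limit (Protocol 8.1), so subjects over 21 are expected.

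The only visible rule on which height to use is in SAP Appendix C. Subjects over 21 at consent take the screening height. Subjects of 21 or younger take the height at the visit or, failing that, the last non-missing one. The list that holds these rules is headed as data handling for spirometry.

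**The concern.** The general rules seem to close off the obvious remedy. SAP 9.1 says that incomplete or missing data "will not be imputed, unless otherwise specified". Note 2 to SAP Table 12-1, whose rows include weight, height and BMI, adds: "If no numerical measurement is available within a visit window, the measurement will be considered missing for the visit". Combine these with a formula that asks for the visit's own height, and a subject over 21 has no post-baseline BMI.

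A second doubt concerns baseline. Subjects over 21 have no Day 1 height, so the last visit with both measurements is Screening. Baseline BMI might then come from a different day than baseline weight.

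BMI at Week 24 is fifth in the hierarchy, and sweat chloride and CFQ-R at Week 4 can be tested formally only if it succeeds (SAP 9.3.2.3). Losing the older subjects would weaken that test and could block the two behind it.

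**Working it through.** The documents state no power, SD or effect size for BMI, so there is no figure to reproduce. The check compares the texts, with one calculation to size the word-for-word reading.

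**1. Inputs scheduled for a subject over 21** (Protocol Tables 3-1 and 3-2)

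| | Screening | Day 1 | Six post-baseline BMI visits |
|---|---|---|---|
| Weight | yes | yes | 6 of 6 |
| Height | yes | no | 0 of 6 |

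On schedule there is one height per subject, so there is nothing to choose between.

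**2. Which subjects the plan means to include.** SAP 9.3.3.2 restricts the BMI z-score model by age and drops a covariate for it: "excluding the covariate of age at screening (<18 versus ≥18 years of age), for subjects ≤20 years of age at Baseline". BMI itself gets neither the restriction nor the dropped covariate. If BMI were available only up to age 21, it would cover almost the same subjects as the z-score, and an unrestricted key secondary endpoint would make little sense. The protocol stops measuring adult height yet plans BMI at six visits. The two fit together only if the screening height is reused.

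**3. The defaults on missing data.** These rules concern a measurement that should exist and does not. Using the one height that the protocol schedules is part of the derivation, not imputation. Appendix C does the same for the same subjects, under the same general rules, to obtain percent predicted FEV1 at every visit.

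**4. Baseline.** SAP 9.1 takes the "most recent non-missing measurement (scheduled or unscheduled) collected before the first dose of study drug in the Treatment Period". Applied to each component, that gives the Day 1 weight and the screening height. SAP Table 12-1 agrees: the baseline window for weight, height and BMI is Day 1 or earlier, so the screening height lies inside it. Then, for a subject over 21 with weight W and screening height H,

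BMI change = W(Week 24)/H² − W(Day 1)/H² = [W(Week 24) − W(Day 1)]/H².

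This is body-weight change rescaled, with the same Day 1 starting point as the body-weight endpoint. The other reading takes the whole BMI from Screening, up to 28 days before first dose, or 28 + 14 = 42 days with the extension in Protocol 9.1.1.3. It arises only if baseline is picked on the derived value alone, which no text requires.

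**5. Population.** Missing outcomes in a repeated-measures model are compatible with a full-analysis-set basis, because SAP 9.3.1.2 expects them. Even the word-for-word reading would reduce the contributing data without contradicting SAP 9.3.

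**6. Size of the word-for-word reading.** SAP 7.2 gives 180 per arm and 10% dropout at Week 24: 180 × 0.90 = 162. The share p over 21 is not in the documents and is assumed here, as is 90% power at 162 per arm (two-sided 0.05, normal approximation).

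- Subjects left per arm = 162 × (1 − p)
- SE ratio = 1/√(1 − p)
- Power = Φ[(1.960 + 1.282) × √(1 − p) − 1.960]

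| Assumed p | Left per arm | SE ratio | Power |
|---|---|---|---|
| 30% | 113 | 1.20 | 77% |
| 50% | 81 | 1.41 | 63% |
| 70% | 49 | 1.83 | 43% |

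With the screening height used, the missing height removes nobody and the expected 162 per arm remain.

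**The case for a change.** The best argument for an amendment is that a gated endpoint should have one reproducible value per subject and visit, fixed before unblinding. The authors saw the height problem for percent predicted FEV1 and wrote a rule; for BMI they did not. That rule also tells the analyst to ignore any later height in a subject over 21, so they foresaw off-schedule heights. Under SAP 9.3.2.1 such a height would enter BMI, while FEV1 at the same visit used the screening value. For subjects of 21 or younger with a missed height, the last-non-missing rule is again written only for spirometry. Two programmers could also differ on baseline.

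The textual part stands: the visible SAP does not say which height BMI uses after age 21. The consequences are slight. An off-schedule height in an adult would be an exception to the schedule and should differ from the screening height by little more than measurement error. A missed height in a younger subject whose weight was taken at the same visit affects single visits, which the model tolerates. The baseline question has a natural answer in SAP 9.1 and Table 12-1. None of these choices depends on treatment arm, so none favours either arm. Finally, SAP 9.1 refers to an internal document of programming rules that is not public, and parts of the SAP are redacted. A BMI height rule may sit there, though that cannot be confirmed.

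**Conclusion.** The definition leaves out a detail that an analyst would supply in only one sensible way: visit weight over the square of the screening height for subjects over 21. With that, BMI exists wherever weight does, baseline BMI matches baseline weight, and the position of the endpoint in the hierarchy is unaffected. A clarifying sentence would be harmless, but it would not be expected to alter a result, so no change is called for.

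This rests on two assumptions: that the analysts follow the convention of Appendix C, and that they apply the baseline rule to weight and height separately. The losses in the table, down to 49 of 162 per arm and 43% power, describe a reading that the rest of the plan rules out. They also depend on assumed age shares and an assumed 90% starting power, so they do not measure a defect in this trial.

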### 9.3.2.2 Analysis Method

Absolute change in ppFEV1 through Week 24: Analysis of this variable will be based on an MMRM that is exactly the same as the primary efficacy variable. However, the Day 15 Visit will not be included in the estimation of the average treatment effect through Week 24 as the treatment effect is not expected to reach the steady state at Day 15.

Number of PEx through Week 24: Analysis of this variable will be performed using a negative binomial regression model with a fixed effect for treatment, as well as continuous baseline ppFEV1, age at screening (<18 versus ≥18 years of age), and sex (male versus female) as covariates. The logarithm of the subject-specific PEx analysis period duration (in years) will be treated as the offset in the model.

Absolute change in SwCl from baseline through Week 24: Analysis of this PD variable will be based on an MMRM similar to the analysis of the primary efficacy variable. Data obtained from Week 4, Week 8, Week 12, and Week 24 Visits will be included in the model and all of these visits will be included in the estimation of the average treatment effect through Week 24.

Absolute change in the CFQ-R respiratory domain score from baseline through Week 24: Analysis of this domain will be based on an MMRM similar to the analysis of the primary efficacy variable. Data obtained from Week 4, Week 8, Week 12, Week 16, and Week 24 Visits will be included in the model and all of these visits will be included in the estimation of the average treatment effect through Week 24.

Absolute change in BMI from baseline at Week 24: Analysis of this variable will be based on an MMRM similar to the analysis of the primary efficacy variable. Data obtained from Day 15, Week 4, Week 8, Week 12, Week 16, and Week 24 Visits will be included in the model.

Absolute change in SwCl from baseline at Week 4: Analysis of this PD variable will be based on an MMRM similar to the analysis of the primary efficacy variable. Data obtained from Week 4, Week 8, Week 12, and Week 24 Visits will be included in the model to estimate the treatment effect at Week 4.

Absolute change in CFQ-R respiratory domain score from baseline at Week 4: Analysis of this domain will be based on an MMRM similar to the analysis of the primary efficacy variable.

Data obtained from Week 4, Week 8, Week 12, Week 16 and Week 24 Visits will be included in the model to estimate the treatment effect at Week 4.

To assess the longitudinal profile of the efficacy and pharmacodynamic assessments with repeated measures up to Week 24, the LS mean (SE) of the within-treatment group change from baseline at each post-baseline visit along with the 95% CI will be estimated from the corresponding MMRM. The LS mean (SE) of the treatment difference between VX-659/TEZ/IVA and triple placebo at each post-baseline visit will be provided along with the corresponding 95% CI and *P* value. The LS mean (SE) at each visit will also be plotted by treatment group. In addition, the post-baseline raw values and the absolute change from baseline at each post-baseline visit will be summarized descriptively (n, mean, SD, median, minimum, and maximum).

### **9.3.2.3 Multiplicity Adjustment**

The Lan and DeMets alpha spending function will be applied to the primary endpoint of the absolute change in ppFEV1 at Week 4 to control the overall type I error rate of 0.05 such that an alpha of 0.01 will be preserved for the final analysis.

If the number of subjects included in the IA is 140, the primary endpoint of the absolute change from baseline in ppFEV1 at Week 4 will be tested at an alpha of 0.044 during the IA. The actual alpha at the IA ( $\alpha_0$ ) will be determined based on the actual number of subjects included in the interim Full Analysis Set. If the study does not cross the efficacy boundary during the IA (*P* value  $\geq \alpha_0$ ), then the primary endpoint will be tested at an alpha of 0.01 at the final analysis when all subjects complete the study participation. See Section 7.5 for more details.

The key secondary endpoints will be formally tested at an alpha of 0.05 at the final analysis when all subjects complete study participation only if the primary endpoint is statistically significant at the IA or at the final analysis. A hierarchical testing procedure will be used to control the type I error rate for the multiple key secondary endpoints tested at an alpha of 0.05. For a test at any step to be considered statistically significant within the testing hierarchy, it must be statistically significant, and all previous tests (if any) within the hierarchy must be statistically significant at the 0.05 level. The testing order of the key secondary endpoints is as follows:

- Absolute change in ppFEV1 from baseline through Week 24
- Number of PEx through Week 24
- Absolute change in SwCl from baseline through Week 24
- Absolute change in CFQ-R respiratory domain from baseline through Week 24
- Absolute change in BMI from baseline at Week 24
- Absolute change in SwCl from baseline at Week 4
- Absolute change in CFQ-R respiratory domain score from baseline at Week 4

